1.3 Primary and Secondary Outcomes

The primary outcome is glycemic control. Glycemic control is difficult to accurately assess whenever antihyperglycemic medications doses change, as changing doses can mask improvements in standard glycemic outcomes. Therefore, we define an individual has having an improvement in glycemic control if s/he needs a lower dose of antihyperglycemic medications (if medication doses change) or has lower mean glucose levels (if medication doses do not change). We will use the following hierarchy of glycemic outcomes:

- 1. Achieving non-diabetic glycemia without antihyperglycemic medications (assessed as a binary outcome and analogous to T2D remission without the 3-month requirement);
- Total dosage of antihyperglycemic medications, as measured by the medication effect score (MES);
- 3. Mean glucose during a three-hour OGTT; and
- 4. Mean 24-hour glucose as measured by continuous glucose monitoring (CGM), adjusted for any changes in medication doses via the MES (see Section 4.5).

We decided to use mean 24-hour glucose as measured by CGM in lieu of HbA1c because CGM more accurately assesses the present glycemic status over the previous week, whereas HbA1c is a lagging indicator of glycemic control. The hierarchy implies that a positive or negative outcome in an upper level will always supersede any findings from lower levels in the hierarchy. In particular, if glucose-lowering medication dosages change, then assessments 1 and

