4.3 Power Calculation

As this is a pilot and feasibility trial, the sample size was not based on a power calculation. We selected a sample size of 16 completers to provide sufficient data to inform the design of a future trial. Nonetheless, our study has 81% power to detect an 18.0% rate of attaining non-diabetic glycemia vs. a spontaneous remission rate of 0.7%.²³ Further, 16 completers provides 80% power to detect effect sizes of Cohen's d ≥ 0.78 , using a two-tailed paired t-test with α =0.05. This corresponds to a large effect size, which we expect, as participants eat a very large amount of fruit. We acknowledge that we are not powered to detect medium or small effect sizes, which may also be clinically relevant.

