4.4 Statistical Analyses

All statistical tests will be two-sided with a Type I error rate of α =0.05. Because this is a controlled-feeding trial—designed to determine the cardiometabolic effects under conditions of nearly perfect adherence—we will analyze the data per protocol in completers only. The primary comparison will be between weeks 0 and 12, with secondary comparisons between weeks 0 and 4 and between weeks 4 and 12. Data may be Winsorized if there are outliers with an overwhelming degree of influence or values that are non-physiologic . We will test whether a fruit-rich diet can induce non-diabetic glycemia without hyperglycemia medications by testing whether our observed "remission" rate differs from the spontaneous T2D remission rate of

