0.07% using an exact binomial test.²³ If there is one or more cases of non-diabetic glycemia, then the true rate is non-zero, and we will report a 95% confidence interval derived from bootstrapping. All other data will be analyzed as change scores. For all continuous data and Likert score data with at least four levels and sufficient variability, we will use linear mixed models with time as either a linear or categorical effect and with a random intercept for participants. For other data types, we will use distribution-appropriate generalized linear mixed models. Alternatively, if spline models are more parsimonious than treating time as a linear or categorical effect, we will use generalized-additive models with penalized adaptive regression splines instead. To analyze the data from CGM, we will perform a trajectory analysis to determine whether there are different "response phenotypes." Since it is conceivable that participants starting from very different baseline diets may have distinct trajectories early on, we may also consider a trajectory analysis of the data with special attention to the Ramp-Up phase and restrict the models to the Main Phase period after the trajectories converge. We will consider adjusting for covariates such as baseline values or mean 24-hour glucose levels only if statistically and clinically merited. For the inferential statistics on continuous variables, we will test for differences using least squares means evaluated at study timepoints, or alternatively, if time is most appropriately treated as a categorical variable, by the significance of the coefficient for each timepoint. We will analyze change in categorical variables using McNemar's test for dichotomous variables and Bowker's test of symmetry for variables with more categories. Finally, to assess inter-individual responses in the vein of precision nutrition, we will also report the percentages of participants who experience an improvement, no change, and a worsening in glycemic control.

5. Protocol Amendments

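### With 16 completers the planned bootstrap interval for non-diabetic glycemia can start at 0 and disagree with the exact test, and no interval is planned for zero cases

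*Combined protocol and SAP*

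**What the plan says.** Section 1.3 puts non-diabetic glycemia without antihyperglycemic medication at the top of the primary-outcome hierarchy, where "a positive or negative outcome in an upper level will always supersede any findings from lower levels".

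Section 4.4 sets the general rule: "All statistical tests will be two-sided with a Type I error rate of α =0.05". It compares the observed rate with a spontaneous remission rate of "0.07% using an exact binomial test". If at least one case occurs, "then the true rate is non-zero, and we will report a 95% confidence interval derived from bootstrapping". It gives no bootstrap type, no number of resamples and no interval for zero cases.

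Section 4.3 states the size and its purpose: "We selected a sample size of 16 completers to provide sufficient data to inform the design of a future trial". It adds that "our study has 81% power to detect an 18.0% rate of attaining non-diabetic glycemia vs. a spontaneous remission rate of 0.7" percent. The null rate therefore differs tenfold between Sections 4.3 and 4.4.

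**The concern.** The bootstrap approximates a sampling distribution by resampling the observed data. With 16 binary values and only a few cases, many resamples contain no case at all, so the lower limit can fall to 0 whatever the number of resamples. Three consequences follow.

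- The interval can contain the null rate that the exact test has just rejected.
- It can contain 0, although the same sentence of the plan says that one case shows the rate is not zero.
- With no cases, the resamples are all identical. The plan avoids that degenerate result by reporting nothing, so the reader has no upper bound.

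The estimate and its limits matter here because the trial is meant to inform a later one, and this endpoint overrides those below it.

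**Working it through.** **Inputs.** n = 16 completers, alternative rate 18%, null rate 0.7% and power 81% (Section 4.3); null rate 0.07%, two-sided α = 0.05, exact binomial test, bootstrap 95% interval if there is at least one case (Section 4.4). The percentile version is an assumption, as the plan names none; other versions are checked in step 4.

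**1. The plan's power figure.** Under 0.7%, P(X ≥ 1) = 1 − 0.993^16 = 0.106 and P(X ≥ 2) = 0.0055, so the test rejects at 2 or more cases. At 18%:

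P(X ≥ 2) = 1 − 0.82^16 − 16 × 0.18 × 0.82^15 = 1 − 0.042 − 0.147 = 0.811.

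This reproduces the stated 81%. Under 0.07%, P(X ≥ 1) = 0.011, so a single case rejects and the power would be 1 − 0.042 = 0.958. The stated power therefore goes with 0.7%.

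**2. Percentile limits.** For k cases, the number of cases in a resample is Binomial(16, k/16). The limits are its 2.5% and 97.5% quantiles divided by 16. The share of resamples with no case is (1 − k/16)^16; when that share exceeds 2.5%, the lower limit is exactly 0.

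| Cases | Resamples with no case | Percentile 95% | Clopper-Pearson 95% | Exact p vs 0.7% | Exact p vs 0.07% |
|---|---|---|---|---|---|
| 0 | 100% | none planned (would be 0–0) | 0–20.6% | 1 | 1 |
| 1 | 35.6% | 0–18.8% | 0.16–30.2% | 0.106 | 0.011 |
| 2 | 11.8% | 0–31.3% | 1.6–38.3% | 0.0055 | 0.00006 |
| 3 | 3.6% | 0–37.5% | 4.0–45.6% | 0.0002 | <0.00001 |
| 4 | 1.0% | 6.3–50.0% | 7.3–52.4% | <0.00001 | <0.00001 |

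Test and percentile interval disagree at 2–3 cases if the null is 0.7%, and at 1–3 cases if it is 0.07%.

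**3. How often.** At a true rate of 18%, P(2 or 3 cases) = 0.489, and 0.489 / 0.811 = 0.603. So about 60% of the rejections counted as power would carry a percentile interval containing 0 and 0.7%. P(1 to 3 cases) = 0.636, P(4 or more) = 0.322 and P(0) = 0.042. At other assumed rates, P(2 or 3 cases) is 18.2% at 5%, 41.7% at 10% and 34.2% at 25%. P(0) is 44% at 5% and 18.5% at 10%.

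**4. Other bootstrap versions, lower limit.**

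| Version | 1 case | 2 cases | 3 cases |
|---|---|---|---|
| Basic | −6.25% | −6.25% | 0 |
| Normal | −5.6% | −3.7% | −0.4% |
| BCa, mid-point ties | 0 | 0 | 6.25% |

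The BCa result depends on how ties with the estimate are counted. Strict counting also gives 0 at 2 cases; counting resamples at or below the estimate gives 6.25% there.

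**5. Coverage.** Given at least one case, percentile coverage at a true rate of 18% is 98.4%. It falls to 85.8% at 18.8%, because 18.8% lies just above the upper limit for one case (3/16 = 18.75%).

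**The case against.** The strongest reply is that the plan says only that it will bootstrap, so the percentile figures describe a method it never names. That limits the 1–3 range and the 60% figure to one version, but it does not clear the plan. At 1 case every version examined reaches 0 or below. At 2 cases all do except BCa with ties counted at or below the estimate. At 3 cases the choice of version decides whether the interval excludes the null, which is a reason to fix the method in advance.

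Second, no decision changes: the test is exact, and a reader with the count could compute an exact interval. This stands, and it limits the severity. Coverage at exactly 18% is also adequate.

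Third, 18% is a power assumption, not a forecast. Section 1.5 cites 46% remission in the study that the eligibility criteria follow; at that rate, 2 or 3 cases would have probability only 2.3%. That study used a very-low-calorie diet, so the figure marks one end of a range. At 10% to 25% the conflict remains common.

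Fourth, the disagreement at 1 case exists only under the 0.07% null, and the stated power points to 0.7%. This is right, so the 1-case conflict carries no separate weight here.

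**Conclusion.** The concern holds. With 16 completers, the percentile bootstrap gives a lower limit of 0 at 1, 2 and 3 cases. At 2 and 3 cases that contradicts the plan's own exact test under either null rate. At the plan's 18% rate this affects 48.9% of trials, or about 60% of those that reject the 0.7% null. At zero cases the plan reports no interval, although 0/16 has an exact upper limit of 20.6% and so remains compatible with 18%.

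The range of 1–3 cases and the 60% share assume the percentile version, exactly 16 completers and, for the share, a true rate of 18%. The lack of an interval at zero cases needs none of these assumptions. The hypothesis test is unaffected. What suffers is the reported precision of the leading primary measure, so this should be corrected but does not invalidate the trial.

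**What to change.** Delete the bootstrap clause in Section 4.4, and with it the condition that at least one case must occur. Replace it with wording such as: *We will report the number of cases out of completers with the exact (Clopper-Pearson) 95% confidence interval, whatever the number of cases, including zero.*

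With n = 16 this interval agrees with the two-sided exact test at all 17 possible counts, under 0.7% and under 0.07%. The change is one sentence and needs no new data. The cost is mild conservatism: coverage is 98.5% at a true rate of 18%. A Wilson interval would also cover zero cases (0–19.4% at 0/16), but Clopper-Pearson matches the planned test more naturally.

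The 0.7% and 0.07% null rates in Sections 4.3 and 4.4 must be reconciled separately; this change does not settle which was intended.

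### The random-intercept model gives every visit contrast one pooled standard error, so the week 0-12 and 0-4 tests of continuous outcomes are miscalibrated unless all visit differences have equal variance

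*Combined protocol and SAP*

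**What the plan says.** Section 4.4 (Statistical Analyses) specifies, for continuous outcomes, linear mixed models with time linear or categorical "and with a random intercept for participants". Inference comes from least squares means at the study timepoints or, with categorical time, "by the significance of the coefficient for each timepoint". The contrasts are named: "The primary comparison will be between weeks 0 and 12, with secondary comparisons between weeks 0 and 4 and between weeks 4 and 12". The error rate is stated: "All statistical tests will be two-sided with a Type I error rate of α =0.05". The section leaves the mean structure open (linear, categorical or spline) but names no random slope, residual covariance, robust standard error or degrees-of-freedom method. It also says that these data will be analysed as change scores, without saying how that combines with the random intercept.

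Section 4.3 (Power Calculation) gives its detectable effect "using a two-tailed paired t-test with" a 5% level, for 16 completers. A paired test uses only the variance of the difference being tested.

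Sections 1.9 and 3.2 say that glucose-lowering doses are left alone before week 10 unless safety requires a change. At the end of week 10, all such drugs are stopped in participants who meet the glucose criterion.

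**The concern.** A random intercept lets participants differ in level but not in how much they change. It implies that the 0-4, 4-12 and 0-12 differences all have the same variance. Several features of the design make that doubtful. The visits are unequally spaced. The intervention changes during the trial: fruit rises over weeks 1-4, and the Mediterranean-style half of the diet starts in week 5. Medication stops selectively after week 10. Section 4.4 itself plans to look for groups of participants with different response trajectories.

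If the variances differ, contrasts with above-average variance get standard errors that are too small, and the others get standard errors that are too large. The p-values and confidence intervals for the primary (0-12) and fruit-alone (0-4) contrasts would then not have their stated 5% and 95% properties. These intervals are also meant to inform a later trial.

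**Working it through.** **Plan's own figure.** Section 4.3 states 80% power at d = 0.78 with 16 completers. Noncentral-t power for a paired test (15 df, noncentrality 0.78 × √16 = 3.12) is 83.0%. Power of 80% needs d = 0.749 at n = 16, or 0.778 at n = 15, so the stated pair matches n = 15. For 16 completers it is slightly conservative.

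**Mechanism.** With n participants complete at three visits, the REML random-intercept standard error of any visit contrast is

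SE = √(V̄ / n), where V̄ is the mean of the sample variances of the three differences, on 30 df.

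This agreed with a fitted mixed model in three simulated datasets to about five decimals. The paired standard error is √(V / n) on 15 df, with V the variance of that difference alone. Calibration therefore depends on r = V / V̄. If r > 1 the test is too liberal; if r < 1 it is too strict.

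**Two worked values of r.** Assume that individual response variance equals residual variance (both 1).
- Response growing linearly over 12 weeks: the 0-4, 4-12 and 0-12 difference variances are 2 + 1/9, 2 + 4/9 and 2 + 1. Their mean is 2.519, so r for 0-12 is 3/2.519 = 1.19.
- Divergence at week 4 that is gone by week 12: the variances are 3, 3 and 2. Their mean is 2.667, so r is 0.75 for 0-12 and 1.125 for 0-4.

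**Simulated type I error.** n = 16, three visits, no true effect, 100,000 trials per case, nominal 5%, 30 df. The covariances are assumed. The three figures in a cell are for response variance 1, 2 and 4 times residual.

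| Pattern of individual response | 0-12 | 0-4 |
|---|---|---|
| Compound symmetry | 5.0% | 5% (equal variances) |
| Grows linearly with time | 7.1, 8.6, 10.6% | 3.4, 2.5, 1.4% |
| Complete by week 4, then held | 6.5, 7.3, 8.5% | 6.4, 7.4, 8.4% |
| Early divergence, half kept at week 12 | 3.9, 3.4, 2.6% | 7.2, 8.9, 10.9% |
| Early divergence, gone by week 12 | 2.6, 1.4, 0.5% | 6.3, 7.3, 8.4% |

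Serial correlation decaying by a factor of 0.8-0.98 per 4 weeks gives 9.6-10.6% for 0-12. A paired t-test stays at about 5% throughout. Under the growing-response and serial-decay covariances, treating time as linear gives 7.3-11.8%, and modelling change scores at weeks 4 and 12 with a random intercept gives 6.6-10.2%. Neither reading removes the problem.

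**MES.** Here the documents supply the pattern. Apart from safety changes, the 0-4 change is zero for everyone, so the 4-12 change equals the 0-12 change. With V the variance of that change:
- V̄ = (0 + V + V)/3 = 2V/3, so the mixed-model statistic is √1.5 = 1.225 times the paired t.
- The 30-df critical value is 2.042. The model rejects once the paired t exceeds 2.042/1.225 = 1.668, which on 15 df is p = 0.116. With a normal reference, 1.96/1.225 = 1.600 corresponds to p = 0.130.
- For normally distributed changes, type I error is therefore about 11.6%.

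**Cost of changing.** If compound symmetry were true, the pooled test (30 df) has 85.5% power at d = 0.78, against 83.0% for the paired test. At d = 0.75 the simulated figures are 82.9% and 80.3%.

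**The case against.** The strongest objection concerns direction. Section 4.4 says, while discussing the continuous glucose monitoring (CGM) data, that "participants starting from very different baseline diets may have distinct trajectories early on", and the same sentence goes on to speak of the trajectories converging. Fruit is already at its full share in week 4, and the Main Phase matches diets across participants. That describes early spread that later narrows, which makes the 0-12 test conservative and the 0-4 test liberal. This stands. A reader might infer from the growing-variance cases alone that the primary test runs at 7-11% and the 0-4 test is over-strict. The documents give no variance or correlation, so they do not support that as a general statement.

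Scope is limited too. A reader might take the whole primary outcome to be affected. Its top level, non-diabetic glycemia off medication, is tested by exact binomial test and supersedes the lower levels. In addition, CGM, blood pressure and lipids are collected at more than three times, so the three-visit, 30-df figures do not describe those outcomes if every measurement enters the model.

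The plan is also silent on residual covariance rather than excluding alternatives. But a random intercept is the only structure it names, and an analyst who follows the text would fit that model. Pilot status lowers the stakes without making a miscalibrated interval acceptable.

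For MES, changes will not be normal, so 11.6% is indicative. The √1.5 factor does not depend on normality; it needs only near-zero change between weeks 0 and 4.

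**Conclusion.** The concern holds for the continuous outcomes: MES, OGTT mean glucose, adjusted CGM glucose and the continuous secondary outcomes. As written, the model ties the standard errors of all visit contrasts together, and the 0-12 and 0-4 tests are correctly sized only if the visit differences share one variance.

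For most outcomes the sign is unknown. Under the assumed covariances, 0-12 type I error ranges from about 0.5-4% (early divergence that converges, with 0-4 then at about 6-11%), through 5% (compound symmetry), to about 7-11% (changes that spread with time). More extreme covariances go beyond this range. For MES, the second level of the primary hierarchy, the direction follows from the plan's own medication rules: the 0-12 standard error is too small by √1.5, provided that safety-driven dose changes before week 4 are rare. This is worth correcting before analysis, but it does not invalidate the trial.

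**What to change.** In section 4.4, state that each prespecified contrast (0-12, 0-4 and 4-12) of a continuous outcome is tested with the paired t-test already assumed in section 4.3, with its matching confidence interval. Equivalently, specify a mixed model on the three scheduled visits with categorical time, an unstructured covariance and small-sample degrees of freedom. With three visits and completers only, this is estimable. For outcomes measured more often, apply the contrast to the week 0, 4 and 12 values, because an unstructured matrix over weekly data is not practical with 16 people. The change-score sentence should be reworded to match.

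The cost is one or two sentences in the plan and at most about 3 power points if compound symmetry truly holds. Power at the stated d = 0.78 with 16 completers is then 83.0%, still above the stated 80%. The change corrects the standard error but not the non-normality of MES changes.

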3.11 Questionnaires

We are assessing diet satisfaction, appetite, food cravings, eating behaviors, mood, quality of life, and depression using questionnaires. At weeks 0, 4, and 12, participants complete the following questionnaires:

- Profile and Mood States-Short Form (POMS-SF): assesses current mood states and total mood disturbances;¹³
- Patient Health Questionnaire-9 (PHQ-9): measures the severity of depression;¹⁴
- CDC's Health-Related Qualify of Life (HRQoL): measures quality of life;¹⁵
- Food Craving Inventory II (FCI-II): measures food cravings for various categories of food;¹⁶
- The fruit subsection and fruit juice questions of the Diet History Questionnaire (DHQ): assesses fruit consumption via a semi-quantitative food frequency questionnaire.¹⁷
 Using the same question format as in the DHQ, we also ask participants how often and how much they eat different subcategories of fruit (i.e., raw, frozen, dried, cooked, and juice);
- The fruit and vegetable questions of the 2007 Food Attitudes and Behaviors (FAB) survey: measures attitudes and behaviors related to fruit and vegetable consumption.¹⁸ We are using most of question 2 (except for Q2A, Q2C, Q2H, Q2I, Q2K, Q2L, Q2P, Q2Q, Q2S, Q2T, Q2V, Q2AA, Q2CC, Q2EE) and questions 3, 4, 5, 6, 7, and 9 from

section 1; questions 24, 29, 30, 31, and 32 from section 4; all questions from section 6 except for Q43; and all questions in section 7;

- Fruit Liking Visual Analog Scales (VAS): a 100-mm VAS custom-designed for this study to assess how much participants like subcategories of fruit (i.e., fresh, frozen, fruit smoothies, dried, cooked, canned, and fruit juice);
- Diet Satisfaction Questionnaire: a series of VAS questions to assess both appetite and diet satisfaction. Specifically, we ask about overall diet satisfaction, food tastiness, energy levels, hunger, fullness, stomach fullness, desire to eat, capacity to eat, cravings, and feelings of deprivation. Appetite-related questions are retrospectively assessed over the past week.

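### With 16 completers, Bowker's test of symmetry is a weak choice for ordered categorical items: it ignores category order and does not show the direction of change

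*Combined protocol and SAP*

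**What the plan says.** Section 4.4 gives three rules that could apply to a questionnaire item with several categories.

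- Continuous and suitable Likert data: "For all continuous data and Likert score data with at least four levels and sufficient variability, we will use linear mixed models".
- Everything else: "For other data types, we will use distribution-appropriate generalized linear mixed models".
- Change in categorical variables: "We will analyze change in categorical variables using McNemar's test for dichotomous variables and Bowker's test of symmetry for variables with more categories".

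The last rule makes no exception for ordered categories. It does not say whether Bowker's test is asymptotic or exact, or how empty pairs of cells are handled. No variable is named under it, and sufficient variability is not defined.

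The same section sets the error rate ("All statistical tests will be two-sided with a Type I error rate of α =0.05") and the analysis set ("we will analyze the data per protocol in completers only"). Section 4.3 fixes the size: "We selected a sample size of 16 completers to provide sufficient data to inform the design of a future trial". Each comparison between two visits therefore has at most 16 pairs.

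Section 3.11 lists the questionnaires. Among them is a fruit section that "assesses fruit consumption via a semi-quantitative food frequency questionnaire", with added questions on the frequency and quantity of fruit subtypes. It also lists fruit and vegetable attitude items and a quality-of-life instrument. Response formats and category counts are not given.

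**The concern.** For an ordered item, the question is whether participants moved up or down the scale between visits. Bowker's test asks something else: whether, for each pair of categories, as many people moved one way as the other. Relabelling the categories leaves the statistic unchanged, so order carries no information. The evidence is also spread over k(k-1)/2 degrees of freedom for k categories, which is costly with 16 people.

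Two things are at stake. A null result on an ordered item may reflect the test and not the data. A significant result need not mean improvement or worsening. In a pilot meant to inform a later trial, either could mislead whoever chooses outcomes for that trial. The two routes for categorical data also leave the choice of test open until results are in view.

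**Working it through.** **Inputs.** At most 16 pairs (Sections 4.3 and 4.4); two-sided α = 0.05 (Section 4.4); effect size d = 0.78 (Section 4.3). The number of categories is not in the documents, so 3 to 6 are shown as an assumed range.

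**The plan's own figures.** Section 4.3 gives none for Bowker's test. Its 81% power for 18.0% against 0.7% is reproduced by an exact binomial rule needing at least 2 of 16: 1 − 0.82^16 − 16 × 0.18 × 0.82^15 = 1 − 0.042 − 0.147 = 0.811. At d = 0.78 and n = 16, the paired t-test has 83% power by the noncentral t; the stated 80% matches n = 15. That difference is conservative and does not bear on this point. I use d = 0.78 only as the plan's own effect size.

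**Bound on the statistic.** Let b and c be the numbers moving each way between two categories. Then Q = Σ (b − c)²/(b + c) over all pairs. Each term is at most b + c, so Q cannot exceed the number of participants who change category, which is at most 16.

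| Categories k | df = k(k−1)/2 | 5% critical value | Fewest changers for p<0.05 | p at Q = 16 |
|---|---|---|---|---|
| 3 | 3 | 7.81 | 8 | 0.001 |
| 4 | 6 | 12.59 | 13 | 0.014 |
| 5 | 10 | 18.31 | 19 (not available) | 0.10 |
| 6 | 15 | 25.00 | not available | 0.38 |

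At the minimum of 8 or 13, all movement within each pair of categories must be in one direction.

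**Other versions of the test, with 16 changers all one way within each pair.**
- If df counts only the m non-empty pairs: p = 0.003 at m = 4, 0.042 at m = 8, 0.067 at m = 9.
- Exact conditional test, p = 2^m × 0.5^16: 0.00024 at m = 4, 0.0156 at m = 10.

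Both versions can therefore reject with five categories.

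**Example of lost information.** With three categories, 7 of 16 improve and none worsen. Standard Bowker has Q = 7 on 3 df, p = 0.072. The exact sign test gives 2 × 0.5^7 = 0.016. With reduced df, Bowker gives 0.008 if one pair of categories is occupied and 0.030 if two are, so this contrast also depends on the version.

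**Example of missing direction.** Four people move from level 1 to level 2 and four from level 3 to level 2. Then Q = 4 + 4 = 8 on 3 df, p = 0.046, although upward and downward moves balance exactly.

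**Simulated power, three categories.** Assumptions: n = 16; latent normal pairs with paired d = 0.78; categories equally likely at baseline; within-person correlation 0.5 (first figure) or 0.7 (second).
- Standard Bowker: about 24% and 14% (independent runs at 0.7 gave 14% to 16%).
- Bowker with df from non-empty pairs: 27% and 22%.
- Exact conditional Bowker: 32% and 22%.
- Exact signed-rank on category scores: 51% and 40%.

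Even the best Bowker version gives up about 18 to 19 points (51 − 32 and 40 − 22). The signed-rank test stayed below 5% rejection when there was no change.

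**The case against.** The strongest reply has four parts.

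1. **Version.** A reader might infer that no variable with five or more categories can ever reach p<0.05. The documents do not support that. The impossibility belongs to the large-sample test with k(k−1)/2 df, and Section 4.4 does not fix the version. Under reduced df or an exact test, or if responses fall in only four of the five categories and the table is built on those, rejection is possible. This part stands.

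2. **Reach.** A reader might also infer that the questionnaires as a whole are affected. Section 4.4 sends well-spread Likert items with four or more levels to linear mixed models. Power comparisons for such items with four or five evenly used categories would mostly describe variables that never meet Bowker's test, so only the three-category comparison is used here. Several instruments are described as scores or visual analog scales and fit the continuous route. The fruit questions may be turned into a computed intake. This part stands too.

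3. **Another route.** The generalized linear mixed model sentence could cover an ordinal model, which would respect order and use all three visits. That is a fair reading, but the plan does not say that it takes precedence over the Bowker sentence. The reply therefore turns one problem into another: two tests for the same variable and no rule for choosing.

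4. **Consequence.** The trial is a pilot, its size was not set by power, and Section 4.3 concedes low power for small and medium effects. This limits the importance of the point. It is not a reason to prefer a less powerful test when a better one costs nothing in data.

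None of these parts makes Bowker's test suitable for ordered categories.

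**Conclusion.** The point holds as a cheap improvement to the analysis of additional outcomes. Bowker's test ignores order and direction in every version. In the standard version it also has no rejection region at 16 completers with five or more categories. For three ordered categories at the plan's own effect size, an order-respecting exact test has roughly 18 to 26 points more power (40 − 22 to 40 − 14), depending on the Bowker version and the correlation.

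These power figures rest on assumed correlations of 0.5 to 0.7, a latent normal scale and evenly used baseline categories, none of which comes from the documents.

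The affected variables would be three-level ordered items, Likert items judged to vary too little, and any non-Likert ordered items analysed as categories. The documents do not list them or give their category counts, so how many there are is unknown. A reader might infer that the glycemic or secondary results are at risk. Nothing in the documents shows a primary or listed secondary outcome depending on Bowker's test.

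**What to change.** Replace the Bowker clause in Section 4.4 with:

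> Change between two time points in ordered categorical variables that do not meet the linear mixed model condition will be tested with the exact (conditional) Wilcoxon signed-rank test on category scores. Bowker's test, with an exact or permutation p-value, will be used only for variables with three or more unordered categories.

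Then state whether this rule or the generalized linear mixed model sentence governs such items, and list the variables under each rule. An ordinal mixed model across all three visits can be kept as a supportive analysis.

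The cost is a few lines of SAP text and a standard exact routine, with no new data and no more participants. The one downside is that scores must be assumed for the categories; their rank order is the natural choice for these items.
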